# 16.1.4 Population Pharmacokinetic Analysis

The PK and covariate data from this study will be analyzed jointly with data from other studies by nonlinear mixed effect approach in order to describe the PK concentration time profile, to identify covariates explaining (part of) the between subject PK variability, and to estimate the residual PK variability.

The population PK analysis plan will be prepared separately and the results will be reported separately from the CSR.

#### Pharmacodynamics (Part C) 16.2

Pharmacodynamic data will be collected in Part C only. All statistical analyses and descriptive summaries of PD data will be performed on the PD Analysis Set.

#### 16.2.1 Statistical Analysis of Pharmacodynamic Parameters

The rational, methodology, analysis, and results about PD parameters measuring and estimating parasite clearance activities, concentrations, and times needed to meet various treatment targets will be described, performed, updated (as appropriate), and reported separately.

The PD parameters of interest, as defined in the Clinical Study Protocol, are as follows:

The parameters MIC and MPC may be derived in the PK/PD modeling (Section 16.2.3).

#### 16.2.2 Statistical Summary of Pharmacodynamic Measurements

The parasitemia data will be descriptively summarized by dose group and measurement time.

Individual parasitemia-time profiles by dose group will be created using the actual measurement time points and the numeric parasitemia data (ie, geometric mean of the subject's replicates, at each time point). Arithmetic mean parasitemia-time profiles by dose group will also be provided using nominal time points. All parasitemia-time plots will be presented on a semi-logarithmic scale.

Overlay plots of individual parasitemia-time profiles (on semi-logarithmic scale) and whole blood concentration-time profiles (on linear scale) will be provided. Overlay plots of arithmetic mean parasitemia-time profiles (on semi-logarithmic scale) and arithmetic mean whole blood concentration-time profiles (on linear scale) will also be provided by dose group.

Any parasitemia data excluded from the PD Analysis Set will be listed and flagged. Additional statistical summaries and presentations of the PD concentration data would be described and reported separately.

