5.2.5 Rescue Medication for Breakthrough Infections

Subjects in Part C will be prescribed an approved regimen for curative therapy for malaria, to assure final parasite clearance, at recrudescence or at the end of the trial. All subjects will receive Riamet; in addition, Primacin 45 mg will be administered to those subjects who have evidence of gametocytemia. *P. falciparum* 3D7, the parasite strain constituting the inoculum, is fully sensitive to both Riamet and Primacin. Loss of sensitivity is regularly checked in vitro.

The curative/rescue drugs will be inventoried prior to the beginning of trial enrollment on trial accountability logs, to document condition upon receipt, including lot numbers. The Investigator or qualified trial personnel designated by the Investigator will ensure that the received drugs are the specified formulation. The trial site Pharmacist or a nominee designated by the Investigator is

responsible for maintaining an accurate inventory and accountability record of drug supplies for this trial.

- Riamet (20 mg artemether and 120 mg lumefantrine) oral tablets. A course of treatment comprises 6 doses of 4 tablets each (total course of 24 tablets) given over a period of 60 hours. Four oral tablets are administered as a single-dose, administered twice daily at 12 hour intervals, ie, time 0, 12 hours, 24 hours, 36 hours, 48 hours, and 60 hours. Each dose of tablets administered orally should be consumed with food
- Primacin (7.5 mg primaquine phosphate) oral tablets: To clear gametocytes of *P. falciparum*, subjects will receive 45 mg as a single dose with food at the end of their Riamet treatment if gametocytes are identified by gametocyte-specific PCR.

Compulsory commencement of clearance medication will occur no later than 21 days after the last dose of M5717. Administration of rescue medications prior to Day 22 will be determined at the Investigator's discretion using the following criteria:

- Failure of clearance: defined as failure to clear parasitemia by at least 10-fold at 72 hours post IMP administration
- Recrudescence: defined as ≥ 5000 blood stage parasites/mL and a 2-fold parasitemia increase within 48 hours, or re-occurrence of malaria symptoms with a malaria clinical score > 6 .

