Early intervention can occur if either poor responses or fast responses are seen following M5717 treatment. This flexibility is designed to ensure subject safety and to avoid subject inconvenience if useful data cannot be obtained. However, pre-emptive rescue treatment can commence whenever deemed necessary by the Investigator.

Subjects will be monitored, either in the trial site, or by telephone for 3 days to ensure adherence to the rescue medication therapy. In any case, safety assessments should be performed prior to administration of the rescue medication and recorded in the eCRF.

Blood and urine samples will be collected for safety evaluation (hematology, biochemistry, coagulation, urinalysis, and CCI) as will blood samples for PK throughout the residential and ambulant period (at time points indicated in Table 3). This will include hematology, biochemistry, ECG, vital signs, physical examination, coagulation profile and urinalysis. However, serology, red blood cell auto-antibodies, and serum storage collection will still be collected at Day 22 regardless of the study day that rescue medications are administered.

CCI

CCI

CCI

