7.4.1 Adverse Events

7.4.1.1 Adverse Event Definitions

Adverse Event

An AE is any untoward medical occurrence in a subject or clinical investigation subject administered a pharmaceutical product, regardless of causal relationship with this treatment. An AE can therefore be any unfavorable and unintended sign (including an abnormal laboratory finding), symptom, or disease temporally associated with the use of a medicinal product, whether or not considered related to the medicinal product.

For surgical or diagnostic procedures, the condition/illness leading to such a procedure is considered as the AE rather than the procedure itself.

The Investigator must assess the severity of AEs according to the QTS as described in the “Toxicity Grading Scale for Healthy Adult and Adolescent Volunteers Enrolled in Preventive Vaccine Clinical Trials”, as follows:

Mild (Grade 1): The subject is aware of the event or symptom, but the event or symptom is easily tolerated.

Moderate (Grade 2): The subject experiences sufficient discomfort to interfere with or reduce his or her usual level of activity.

Severe (Grade 3): Significant impairment of functioning: the subject is unable to carry out his or her usual activities.

Potentially Life-Threatening (Grade 4): Extreme limitation to daily activity. Significant assistance required. Significant medical intervention, hospital or hospice care very likely.

Investigators must also systematically assess the causal relationship of AEs to the IMP or inoculum using the following definitions. Decisive factors for the assessment of causal relationship of an AE to the IMP include, but may not be limited to, temporal relationship between the AE and the IMP,

known (from animal studies) side effects of the IMP, known side effects of the inoculum, medical history, concomitant medication, course of the underlying disease, trial procedures.

Unrelated: Not reasonably related to the IMP or inoculum or rescue medication. AE could not medically (pharmacologically/clinically) be attributed to the IMP/inoculum/rescue medication under investigation in this clinical trial protocol. A reasonable alternative explanation must be available.

Related: Suspected to be reasonably related to the IMP or inoculum or rescue medication. AE could medically (pharmacologically/clinically) be attributed to the IMP/inoculum/rescue medication under investigation in this clinical trial protocol.

The outcome should be entered with terms described below:

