8.5.2.3 Pharmacodynamics

Part C

The primary PD variable is the PRR of asexual parasites based on qPCR after administration of M5717. Secondary PD variables are PCT, MIC, Pct½, and MPC (calculation to be described in the SAP), clinical score, and the number and percentage of subjects with recrudescence. Statistically, recrudescence is defined as an increase in parasitemia > 1 log₁₀ over 2 or more consecutive qPCR results. To be considered recrudescence this increase must occur after the initial decrease in parasitemia post-IMP administration.

The PRR for asexual parasites will be estimated using the slope of the optimal fit of the log-linear relationship of the parasitemia decay based on the PD Analysis Set. The optimal fit can be derived using summarized replicate parasitemia data, which have been cleaned by dealing with potential outliers, values below the limit of detection and nondetectable values (ND). The optimal fit of the log-linear parasitemia-by-time relationship is determined by using left and right censoring to systematically remove the potential lag phase and tail phase of the parasitemia decay. The decay rate, estimated by the slope coefficient from the log-linear decay regression of qPCR data, will be calculated for each subject. The overall cohort-dose specific PRR will be estimated with its 95% CI by calculating the weighted average slope estimate and corresponding standard error (SE) using an inverse-variance method. Only subjects who have optimal regression models with appropriate fit contribute toward the dose-specific PRR.

For any replicate parasitemia values below LLOQ, the value is substituted with LOQ/2. The LOQ is assumed to be 64 parasites/mL of blood, based on published data (9). For any values that were not detected (ND) the value is set to 1, such that when the data is log₁₀ transformed the ND = log₁₀(1) = 0. If all replicates for a subject within a time point are ND, the first time point with all ND is included in model fitting, and all subsequent time points are set to 'missing', regardless of whether parasitemia values increased afterwards due to potential recrudescence of malaria infection. The data used for all subsequent model selection and fitting calculations is comprised of arithmetic mean of the replicate log₁₀ parasitemia value per time point per subject up to the first time all replicates are ND.

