# Presentation of Continuous and Qualitative Variables for Demographics, Other Baseline Characteristics, and Safety

Continuous variables will be summarized using descriptive statistics, ie:

- number of subjects, number of subjects with non-missing values
- mean, standard deviation (SD)
- median, 25th Percentile 75th Percentile (Q1-Q3)
- minimum (Min) and maximum (Max).

Qualitative variables will be summarized by counts and percentages.

Unless otherwise stated, the calculation of proportions will be based on the number of subjects in the analysis set of interest. Therefore, counts of missing observations will be included in the denominator and presented as a separate category.

When the analysis refers only to certain visits, percentages will be based on the number of subjects still present in the study at that visit, unless otherwise specified.

Mean, Median, Q1, Q3, Min, and Max will have the same precision as collected for SDTM datasets for non-derived data. Standard deviation will be presented with one digit more than the mean. Statistics on derived data will be rounded to reasonable digits whereas maximal digits should be

available in Analysis Data Model (ADaM) datasets. Percentage and percent change from baseline will be reported using 1 decimal digit, if not otherwise specified.

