#### 15.1 Adverse Events

All AEs recorded during the course of the study will be coded with the MedDRA, Version 20.1, and assigned to a System Organ Class (SOC) and a PT.

Treatment-emergent AEs (TEAEs) are those events with onset dates on or after the first IMP administration. Any AE occurring before the IMP administration on Day 1 and resolved before IMP administration or not worsening after IMP administration will be included in the AE listings, but will not be included in the summary tables (unless otherwise stated). These will be referred to as "pre-treatment" AEs.

In case AE-related dates are partial, the available information will be used in a conservative approach to determine whether the AE is treatment-emergent.

All analyses described in this section will be based on TEAEs if not otherwise specified.

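### The SAP sets no cut or split at rescue in its visible Part C analyses, so data collected after Riamet are summarized under M5717 dose groups

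*SAP*

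**What the plan says.** **Rescue.** Protocol 5.2.5 gives Riamet to all Part C subjects, starting at the latest 21 days after the last M5717 dose. Earlier rescue is at the Investigator's discretion. One criterion is "Failure of clearance: defined as failure to clear parasitemia by at least 10-fold at 72 hours post IMP administration". The other is recrudescence: at least 5,000 parasites/mL with a 2-fold rise within 48 hours, or returning symptoms with a clinical score above 6. The same section adds "Early intervention can occur if either poor responses or fast responses are seen following M5717 treatment" and allows pre-emptive rescue at any time. SAP 12.2 lists rescue medication by subject; no other SAP section uses it.

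**Parasitemia.** SAP 16.2.2 states "The parasitemia data will be descriptively summarized by dose group and measurement time" and "Arithmetic mean parasitemia-time profiles by dose group will also be provided using nominal time points", plotted on a semi-logarithmic scale. Neither sentence mentions rescue. SAP 16.2.1 leaves the PD parameter methods to a separate document.

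**Recrudescence for analysis.** Protocol 8.5.2.3 requires a rise of more than 1 log10 over two or more consecutive qPCR results, and "To be considered recrudescence this increase must occur after the initial decrease in parasitemia post-IMP administration". Rescue is not mentioned there, nor in the visible text on the PRR fit.

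**Safety.** SAP 15.1 states "Treatment-emergent AEs (TEAEs) are those events with onset dates on or after the first IMP administration", with no end date. SAP 15 and 15.1.1 tabulate by part and dose. Protocol 7.4.1.1 defines an adverse event as related when it is "Suspected to be reasonably related to the IMP or inoculum or rescue medication". Protocol 7.4.1.2, by contrast, asks for the causal relationship with the IMP or rescue medication, and SAP 15.1.1 treats a missing, unknown or positive relationship as IMP-related.

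**The concern.** Riamet is an effective antimalarial with its own adverse effects, and in Part C its use is planned for everyone. An analysis that labels results only by M5717 dose and does not mark when Riamet began mixes the effects of the two drugs.

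The subjects rescued early are the poor or unusual responders, who carry much of the information on where M5717 stops working. Protocol 5.2.4 says the Part C parasite results will inform the dose range for patients, and PRR is a primary endpoint. If post-rescue counts stay in, clearance by Riamet can be read as clearance by M5717. If adverse events after Riamet stay in the M5717 columns, the tolerability of the study drug cannot be read from the table.

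**Working it through.** The plan states no figure to reproduce here. Part C is descriptive, with up to 3 cohorts of 8 (3 × 8 = 24 subjects).

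1. **Safety window.** After a single dose, compulsory rescue falls on Day 22 (504 h) and the End of Trial visit on Day 44 (1,032 h). Share of follow-up after rescue: (44 − 22)/(44 − 1) = 22/43 = 51%; in hours, (1,032 − 504)/1,032 = 528/1,032 = 51%. The Day 29, 33 and 44 visits therefore follow Riamet for every single-dose subject. This is a share of days, not of events.

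2. **Parasitemia summaries.** Protocol 5.2.4 plans qPCR until Day 22, so post-Riamet counts come only from subjects rescued before then. One such subject is 1/8 = 12.5% of a cohort. The parasiticidal assessment in Protocol 7.3 runs to Day 8 (168 h). A subject rescued at 72 h contributes 168 − 72 = 96 h, about 4 days, of post-Riamet time to it.

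3. **PRR fit.** The visible text stops at the first time point with all replicates not detected. A subject rescued for non-clearance has not reached that point, so the rule does not remove post-rescue data. As an illustration, I simulated a subject rescued at 72 h. Assumptions: start at 4 log10/mL; true M5717 fall 0.0 to 0.6 log10 per 48 h; post-rescue fall 1.5 to 3.5; residual SD 0.15 or 0.30; 40 replicates per setting. The window rule and qPCR schedule are redacted, so I chose the window with the smallest p-value (at least 4 points) and assumed sampling times.
   - No cut: every fit passed the p < 0.001 criterion, with median fitted falls of about 0.8 to 2.0.
   - Cut at rescue: 0–7% of fits passed when the true fall was 0.0, 10–55% when it was 0.3, and 47–100% when it was 0.6.

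4. **Two definitions of recrudescence.** A 2-fold rise is log10(2) = 0.30. The statistical rule needs more than 1. For rescue at 5,000/mL the rise is log10(5,000/nadir):

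| Nadir (/mL) | Rise (log10) | Exceeds 1? |
|---|---|---|
| 100 | 1.70 | yes |
| 499 | 1.001 | yes |
| 500 | 1.00 | no |
| 1,000 | 0.70 | no |
| 2,500 | 0.30 | no |

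The statistical rule is met only if the nadir was below 5,000/10 = 500/mL.

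5. **Effect on the percentage.** Assume 8 subjects, 2 with recrudescence and 3 rescued for non-clearance. Exact 95% intervals are in brackets.
   - Non-clearers as non-events: 2/8 = 25% (3.2–65.1%).
   - Excluded: 2/5 = 40% (5.3–85.3%).
   - Counted as failures: 5/8 = 62.5% (24.5–91.5%).

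6. **Mean profile.** Assume seven subjects at 32/mL (half the LOQ of 64) and one at 20,000/mL. Arithmetic mean: (7 × 32 + 20,000)/8 = 2,528. Geometric mean: 10^[(7 × 1.505 + 4.301)/8] = 10^1.855 = 72. One subject sets the arithmetic curve.

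**The case against.** The strongest reply is that much of the PD analysis is not in view. SAP 16.2.1 and 16.2.3 send PD parameters and PK/PD modeling to separate documents, and parts of the protocol's PD text are redacted, so a rescue rule for PRR or recrudescence may exist there. SAP 8.1 and 8.2 also allow affected PD data or subjects to be excluded. This limits what can be said about PRR and recrudescence. It does not reach SAP 16.2.2 or Section 15, which are live analyses, and rescue is not named among the excludable events.

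A reader might infer that subjects rescued for non-clearance will be reported as having no recrudescence. The documents do not say so. The rule that "the calculation of proportions will be based on the number of subjects in the analysis set of interest" stands under a heading for demographics, baseline and safety, and non-clearance is by definition a different outcome from recrudescence. The protocol synopsis also summarizes absence of parasitemia separately. What stands is that no counting rule is written.

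Other limits also stand:
- Laboratory and ECG tables are by time point (SAP 15.3, 15.5.1), so visits after Day 22 are already separate. Only early-rescued subjects mix pre- and post-Riamet values at one visit.
- The eCRF, unseen here, may record IMP causality separately.
- The two definitions partly overlap with non-clearance. The 72-hour count cannot be below the nadir, so anyone whose pre-dose count was under 10 times the nadir has also failed the 72-hour criterion.
- The arithmetic mean is a separate display matter, and individual profiles are plotted too.

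**Conclusion.** The point holds as a gap in analysis rules and should be corrected before lock. It is firmest for adverse events: rescue is universal, 51% of single-dose follow-up comes after it, and nothing in that section is deferred. It is also firm for the parasitemia summaries in SAP 16.2.2, but limited to subjects rescued before Day 22. For PRR it rests on the visible protocol text and on a simulation with assumed rates, schedule and window rule. For recrudescence, the threshold mismatch is plain arithmetic; the 25%, 40% and 62.5% figures use invented counts and show only how much the unwritten choice can matter.

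A reader might go further and infer that the recrudescence percentages could reverse the dose order or misdirect the next cohort's dose. The documents do not support that. SMC analyses fall under the SMC Charter (SAP 6.1), SAP outputs follow database lock (SAP 6.2), and MIC may come from modeling. Nor does the SAP disregard rescue altogether, since it lists it by subject.

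**What to change.** Changes to the analysis only:

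1. End Part C parasitemia summaries, plots and PRR and PCT fits at the first rescue dose. List and flag later data. Carry the same rule into the separate PD document.
2. Place each subject in one mutually exclusive Day-22 category: non-clearance, recrudescence by either definition, rescued for another reason, or none. Fix an order of precedence for subjects who meet more than one. Reconcile Protocol 5.2.5 and 8.5.2.3 for analysis purposes.
3. Split Part C TEAE tables into before and after first Riamet. Flag post-rescue laboratory and ECG values in early-rescued subjects. Base IMP-related tables on causality to the IMP alone.
4. Use geometric means across subjects for parasitemia profiles, as SAP 16.2.2 already does for replicates.

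A Kaplan-Meier analysis is not advised. Early intervention is tied to response, so censoring at pre-emptive rescue would be informative, and 8 subjects per cohort add little beyond the category table.

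The cost is SAP wording and some programming; rescue data are already collected. A small eCRF clarification is needed if IMP causality is not recorded separately. The downside is fewer late observations in the M5717 summaries. Rescue criteria are unchanged.

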#### 16.2.3 PK/PD Modeling

The methodology for PK/PD modeling will be defined in a separate analysis plan and will be reported in a PK/PD modeling report separated from the CSR.

